#### 6.1.3 Guidelines for screening, monitoring and management of HBV/HCV reactivation

HBV screening tests, on study monitoring, and management of HBV reactivation:

1. All patients must be screened with HBV serologic markers: HBsAg, HBsAb, and HBcAb.

- 2. If HBsAg and/or HBcAb are positive, test for HBV-DNA.
- 3. Refer to Table 6-5 for actions to be taken based on screening HBV results.
- 4. If a patient is HBsAg positive or HBV-DNA positive BUT is not on antiviral therapy:
  - a. Consult a physician with expertise in managing HBV
  - b. Initiate antiviral therapy with entecavir 0.5mg QD 1-2 weeks prior to first dose of EGF816 treatment.
  - c. If a patient cannot take entecavir, contact the principal investigator to select an appropriate antiviral therapy.
  - d. If antiviral therapy cannot be given, the patient is not eligible for the study.
  - e. During the study, monitor HBV-DNA every 12 weeks (or more frequently if clinically indicated). (Refer to Table 6-6 if there is evidence of viral reactivation on study)
  - f. Antiviral therapy should continue for at least 4 weeks after the last dose of EGF816.
- 5. Patients who are HBsAg positive or HBV-DNA positive at screening and already have been receiving antiviral therapy are eligible provided the patient remains on antiviral treatment.
  - a. Identify a consulting physician with expertise in managing HBV who can provide treatment guidance, if required, while the patient is on study.
  - b. HBV-DNA should be monitored every 12 weeks (or more frequently if clinically indicated).
  - c. Antiviral therapy should continue for at least 4 weeks after the last dose of EGF816.
- 6. Refer to Table 6-6 for guidelines of management for HBV reactivation.

Test	Result	Result	Result	Result	Result
HBV-DNA	+	+ or -	-	-	-
HBsAg	+ or -	+	-	-	-
HBsAb	+ or -	+ or -	+ and no prior HBV vaccination	- or + with prior HBV vaccination	- or + with prior HBV vaccination
HBcAb	+ or -	+ or -	+ or -	+	-

Table 6-5: Actions to be taken based on hepatitis B results screening

NCI Protocol #: DF/HCC Protocol #: 17-291 Protocol Version Date: January 10th, 2019

Test	Result	Result	Result	Result	Result
Required actions	* Consult a physician with expertise in managing HBV. After the consultation, antiviral therapy should be started 1-2 weeks			ral therapy. IBV-DNA eeks.	No antiviral therapy.

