	
 
prior to 1st dose of EGF816 treatment.
 
Recommended antiviral therapy is entecavir 0.5mg QD. Contact the study PI if a patient cannot take entecavir.
 
Monitor HBV-DNA every 12 weeks (or more frequently if clinically indicated).
 
Antiviral therapy should continue for at least 4 weeks after the last dose of EGF816.
 
				HBV-DNA screening not required unless HBsAg and/or HBcAb are positive

Table 6-6 Guidelines for management of HBV reactivation

HBV reactivation (with or without clinical signs and symptoms)*			
Screening test results	Monitoring test results that define HBV reactivation	Actions to be taken	
Positive HBV- DNA OR	Increase of 1 log in HBV-DNA relative to screening HBV- DNA value	Interrupt EGF816 and gefitinib treatment. Assess patient compliance with antiviral therapy. Consult a physician with expertise in managing HBV and consider changing antiviral therapy.	
Positive HBsAg	OR New appearance of measurable HBV- DNA	
 
While patient is on antiviral therapy, continue interruption of EGF816 administration until resolution to:
 
≤ screening HBV-DNA levels and
 
≤ grade 1 ALT (or baseline ALT, if > grade 1) if ALT elevation was observed
 
	
		
 
If resolution occurs within ≤ 21 days EGF816 and gefitinib should be re-started, one at a time, at the same dose level unless dose reduction/interruption is indicated due to any other reason. Resume EGF816 first with close LFT monitoring. Resume gefitinib if LFTs remain ≤ grade 1 after at least 7 days of EGF816. Antiviral therapy should continue for at least 4 weeks after the last dose of EGF816.
 
If resolution occurs > 21 days, contact study PI for approval of restarting of EGF816 and gefitinib is approved: follow the same guidelines as above.
 
If restarting of EGF816 and gefitinib is NOT approved: discontinue study treatment. Continue antiviral therapy for at least 4 weeks after the last dose of EGF816
 
Monitor HBV-DNA every 12 weeks (or more frequently if clinically indicated).
 
	

Screening test results	Monitoring test results that define HBV reactivation	ical signs and symptoms)* Actions to be taken
Negative HBV- DNA	New appearance of measurable HBV- DNA	Interrupt EGF816 and gefitinib treatment. Consult a physician with expertise in managing HBV. After the consultation, start antiviral therapy.
AND		While patient is on antiviral therapy, continue interruption of EGF816 and gefitinib

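### Table 6-6 judges HBV reactivation and recovery against a screening HBV-DNA value that is pre-antiviral in some patients and on-antiviral in others, so one rule sets two different triggers

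*Combined protocol and SAP*

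**What the plan says.** Section 6.1.3 separates two groups of HBV-positive patients.

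- **Step 4** begins: "If a patient is HBsAg positive or HBV-DNA positive BUT is not on antiviral therapy". For these patients step 4b says: "Initiate antiviral therapy with entecavir 0.5mg QD 1-2 weeks prior to first dose of EGF816 treatment". The antiviral is started because of the screening result, so the screening HBV-DNA value is taken before antiviral therapy.
- **Step 5** covers patients positive at screening who "already have been receiving antiviral therapy are eligible provided the patient remains on antiviral treatment". Their screening value is already an on-antiviral value.

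The first row of Table 6-6 covers both groups. Reactivation is either of two results:

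- "Increase of 1 log in HBV-DNA relative to screening" value
- "OR New appearance of measurable HBV- DNA"

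If either is met, both study drugs are held, adherence to the antiviral is checked, an HBV physician is consulted and a change of antiviral is considered. The hold ends when HBV-DNA is "≤ screening HBV-DNA levels" and any ALT rise has settled. The table's footnote makes every reactivation an SAE.

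For step 4 patients the monitoring rule is "During the study, monitor HBV-DNA every 12 weeks (or more frequently if clinically indicated"); step 5 patients have the same interval. Neither section 6.1.3 nor the study calendar (Table 10-1) provides for a new HBV-DNA reference after the antiviral is started.

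**The concern.** A change-from-reference rule means the same thing in two groups only if the reference is taken under the same conditions. Here it is not. In a step 4 patient the reference is the level the antiviral is meant to lower; in a step 5 patient it is the lowered level.

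The first actions in Table 6-6 are to check adherence and reconsider the antiviral, so the table is meant to pick up failure of antiviral control. Yet a step 4 patient who stops the antiviral and returns to the untreated level has risen by zero over screening.

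At stake are the hold of both study drugs, the decision to restart them, and the reactivation SAE. The same on-study rebound can count as an event in one group and not in the other.

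**Working it through.** The plan states no figure here that could be reproduced. The check is arithmetic on the table's own rule.

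**Inputs**
- S: screening HBV-DNA in log10 units. Not given; examples 3, 5 and 7.
- N: lowest on-antiviral level. Not given. The fall after screening is k = S − N, assumed 1 to 4.
- Detection limit: not given; assumed 1 log.
- Trigger for the first criterion: S + 1 (Table 6-6).

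**First criterion.** The rise needed from the on-antiviral level is (S + 1) − N = k + 1 logs.

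| Fall k | Rise needed | Fold | Screening level needed for DNA to stay measurable |
|---|---|---|---|
| 0 (stable step 5 patient) | 1 log | 10 | above 1 |
| 1 | 2 logs | 100 | above 2 |
| 2 | 3 logs | 1,000 | above 3 |
| 3 | 4 logs | 10,000 | above 4 |
| 4 | 5 logs | 100,000 | above 5 |

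The last column is k plus the assumed detection limit of 1. Outside that condition the patient becomes unmeasurable and the second criterion comes into play.

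**Examples with measurable low points**
- S = 7, N = 3: trigger at 8. A rebound of just under 8 − 3 = 5 logs meets neither criterion.
- S = 5, N = 2: trigger at 6. Just under 6 − 2 = 4 logs goes unflagged.
- S = 3, N = 2: trigger at 4. Just under 4 − 2 = 2 logs goes unflagged.

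**Same rebound, two groups.** Take two patients at 3 logs on antiviral therapy who both rise to 7. The step 5 patient was screened at 3, so the rise over screening is 7 − 3 = 4 logs and the event is recorded. The step 4 patient was screened at 7, so the rise is 7 − 7 = 0 and no event is recorded.

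**Second criterion.** The table does not say what the new appearance is measured against.
- Read as new on study: it fires at the first measurable result after an unmeasurable one, whatever S is. The unmeasurable result has to have been observed, and scheduled tests are 12 weeks apart.
- Read against screening: a patient who was HBV-DNA positive at screening can never meet it.
- An HBsAg-positive patient who was HBV-DNA negative at screening is covered under either reading.

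**Restart condition.** It uses the same screening value. With S = 7 and N = 3, the HBV-DNA part of recovery is satisfied at 7, which is 7 − 3 = 4 logs above the earlier on-antiviral level. A step 5 patient screened at 3 has to return to 3.

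**The case against.** Steps 4 and 5 and Table 6-6 do not contradict each other in words; a screening reference throughout may be deliberate. That is fair, but the plan does not say so, and the effect is to give one criterion two meanings.

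The second criterion is a real safeguard. Read as new on study, it catches every rebound from an observed unmeasurable level. The larger the assumed fall, the likelier HBV-DNA is to become unmeasurable, so the 10,000- and 100,000-fold figures apply only to patients whose screening load was high enough. This stands and limits the point.

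A reader might infer more than the documents support:

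- **That the drugs would simply continue.** Table 6-4 holds both drugs for isolated Grade 3 or 4 AST/ALT elevation whatever the HBV-DNA, and section 6.1 lets the investigator modify the guidelines in individual cases. What can be said is that Table 6-6 itself does not call for a hold. The HBV-DNA re-test triggered by ALT is no separate remedy, because its result is judged by Table 6-6 again.
- **That SAEs are undercounted.** A rebound meeting the general criteria in section 7.2 is an SAE regardless. Some virological events may go unlabelled; an undercount is possible, not shown.
- **That step 4 patients are less protected overall.** Step 4a requires consultation with an HBV physician, while step 5a only requires that one be identified. HBV-DNA may also be tested more often in both groups if clinically indicated.
- **That the treatment-related HBV reactivation death in section 2.2.2 shows this mechanism.** That section gives no screening status, antiviral use or HBV-DNA course for the patient.

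**Conclusion.** The concern holds in a limited form. The reference for the 1-log criterion and for restart is pre-antiviral in step 4 patients and on-antiviral in step 5 patients. Where HBV-DNA falls by k logs but stays measurable, the first criterion needs k + 1 logs instead of 1, and a return to the untreated level meets neither criterion. Table 6-6 then calls for neither a hold nor a reactivation SAE. The gap is wider if the second criterion is read against screening, which the text leaves open.

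The mismatch follows from the documents alone. Its size rests on the assumed k of 1 to 4, screening levels of 3 to 7 logs and a detection limit of 1 log. The number of affected patients is not given and is likely to be few of the 36. The primary endpoint analysis is not at issue. The point still deserves correction, because following Table 6-6 exactly can leave a safety event unrecognised.

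**What to change.** The sponsor, with HBV expertise, should reconcile steps 4 and 5 of section 6.1.3 with Table 6-6. Three things need to be stated, each with the same meaning for patients who start antivirals after screening and for those already on them:

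- the reference for the 1-log criterion;
- what new appearance of measurable HBV-DNA is measured against;
- the HBV-DNA condition for ending the hold.

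The choice of reference value and threshold belongs to the sponsor and the HBV expert; none is proposed here.

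The cost is a wording change, and possibly some additional interruptions or SAE reports in a few patients.

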# HCV screening tests, on study monitoring, and management of HCV reactivation

- 1. Screen all new patients for HCV-Ab. If HCV-Ab is detected then check HCV-RNA.
- 2. Only patients with negative HCV-Ab or with positive HCV-Ab but **undetectable** level of HCV-RNA are eligible to be enrolled in the study (assuming all other eligibility criteria are met). Patients with detectable HCV-RNA are not eligible to be enrolled in the study.

- 3. Patients with known history of HCV infection and undetectable HCV-RNA at screening should be monitored every 8 weeks (or more frequently if clinically indicated) with HCV RNA-PCR for HCV reactivation.
- 4. Refer to Table 6-7 for definition of HCV reactivation and the management guidelines.

HCV reactivation (	HCV reactivation (with or without clinical signs and symptoms) 			
Screening test results	Monitoring test results that define HCV reactivation	Action to be taken		
Knowledge of past hepatitis C infection with no detectable HCV- RNA	New appearance of detectable HCV-RNA	Interrupt EGF816 and gefitinib treatment. Consult a physician with expertise in managing HCV. After the consultation, start antiviral therapy.		
		While patient is on antiviral therapy, continue interruption of EGF816 and gefitinib administration until resolution to:		
		
 
no detectable HCV-RNA and
 
≤ grade 1 ALT (or baseline ALT, if > grade 1) if ALT elevation was observed.
 
		
		
 
If resolution occurs within ≤ 21 days EGF816 should be re-started at the same dose level unless dose reduction/interruption is indicated due to any other reason. Reintroduce EGF816 first; if LFT remains < grade 1 after at least 7 days on EGF816, resume gefitinib.
 
If resolution occurs > 21 days Contact study PI for approval of restarting of EGF816.
 
If restarting of EGF816 and gefitinib is approved: follow the same guidelines as above.
 
If restarting of EGF816 and gefitinib is NOT approved: permanently discontinue the patient from EGF816 treatment
 
		
		Monitor HCV-RNA every 8 weeks (or more frequently if clinically indicated)		

# Table 6-7 Guidelines for management of HCV reactivation

 All reactivations of HCV are to be recorded as serious adverse event (SAE). Date of viral reactivation is the date on which the defined lab results for reactivation were met (e.g., for a patient whose HCV-RNA was detectable on 01-JAN-15 and ALT reached > 5 x ULN on 22-JAN-15, the date of viral reactivation is 22-JAN-15).

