Negative HBsAg		administration until resolution to:
		
 
≤ baseline HBV-DNA levels and
 
≤ grade 1 ALT (or baseline ALT, if > grade 1) if ALT elevation was observed If resolution occurs within ≤ 21 days EGF816 and gefitinib should be re-started at the same dose level unless dose reduction/interruption is indicated due to any other reason. Reintroduce EGF816 first; if LFT remains ≤ grade 1 after at least 7 days on EGF816, resume gefitinib. Antiviral therapy should continue for at least 4 weeks after the last dose of EGF816. If resolution occurs > 21 days Contact study PI for approval of restarting of EGF816.
 

		If restarting of EGF816 and gefitinib is approved: follow the same guidelines as above.
		If restarting of EGF816 and gefitinib is NOT approved: discontinue EGF816 treatment. Continue antiviral therapy for at least 4 weeks after the last dose of EGF816.
* All pageting of	HRV are to be recorded as	Monitor HBV-DNA every 12 weeks (or more frequently if clinically indicated).

\* All reactivations of HBV are to be recorded as serious adverse event (SAE). Date of viral reactivation is the date on which the defined lab results for reactivation were met (e.g. for a patient who was HBV-DNA positive on 01-JAN-15 and whose ALT reached > 5 × ULN on 01-APR-15, the date of viral reactivation is 01-APR-15).

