# 7.2.3 Reporting to Novartis

To ensure patient safety, every SAE, regardless of suspected causality, occurring after the patient has provided the main informed consent and until at least 30 days after the patient has stopped study treatment must be reported to Novartis within 24 hours of learning of its occurrence. Any SAEs experienced after this 30 days period should only be reported to Novartis if the investigator suspects a causal relationship to the study treatment. Recurrent episodes, complications, or progression of the initial SAE must be reported as follow-up to the original episode within 24 hours of the investigator receiving the follow-up information. An SAE occurring at a different time interval or otherwise considered completely unrelated to a previously reported one should be reported separately as a new event.

Information about all SAEs is collected and recorded on the Serious Adverse Event Report Form; all applicable sections of the form must be completed in order to provide a clinically thorough report. The investigator must assess and record the relationship of each SAE to each specific study treatment (if there is more than one study treatment), complete the SAE Report Form in English, and send the completed, signed form by fax within 24 hours to the oncology Novartis Drug Safety and Epidemiology (DS&E) department - [contact]).

The original copy of the SAE Report Form and the fax confirmation sheet must be kept with the case report form documentation at the study site.

Follow-up information is sent to the same contact(s) to whom the original SAE Report Form was sent, using a new SAE Report Form stating that this is a follow-up to the previously reported SAE and giving the date of the original report. Each re-occurrence, complication, or progression of the original event should be reported as a follow-up to that event regardless of when it occurs. The follow-up information should describe whether the event has resolved or continues, if and how it was treated, whether the blind was broken or not, and whether the patient continued or withdrew from study participation.

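### The worked examples under Tables 6-6 and 6-7 date viral reactivation by an ALT threshold that neither table uses to define it, 21 days later than the table gives in the HCV case

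*Combined protocol and SAP*

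**What the plan says.** Table 6-7 has a column for the monitoring result that defines HCV reactivation, with a single entry: "New appearance of detectable HCV-RNA". The table applies "with or without clinical signs and symptoms". Table 6-6 carries the same qualifier. For patients positive at screening (HBV-DNA or HBsAg) it gives two alternative criteria, "Increase of 1 log in HBV-DNA relative to screening HBV- DNA value" or newly measurable HBV-DNA. For patients negative on both, only newly measurable HBV-DNA counts.

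In both tables ALT appears only among the conditions for resolution, and only where it had risen. The paragraph on LFT monitoring for all patients, also in Section 6.1.3, gives ALT above 5 x ULN another role (8 x ULN for those with a higher baseline). It prompts immediate viral re-testing, and the result is then judged against Table 6-6 or 6-7.

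Both footnotes make every reactivation an SAE and state a general rule: "Date of viral reactivation is the date on which the defined lab results for reactivation were met". Each then illustrates it. The HCV illustration is a patient "whose HCV-RNA was detectable on 01-JAN-15 and ALT reached > 5 x ULN on 22-JAN-15, the date of viral reactivation is 22-JAN-15". The HBV illustration is a patient who was HBV-DNA positive on 01-JAN-15 and whose ALT passed 5 x ULN on 01-APR-15, and it concludes that "the date of viral reactivation is 01-APR-15".

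**The concern.** The rule and its illustration disagree within one sentence, in both footnotes. The rule points to the virological result in the defining column, and the illustration points to an ALT threshold that is not in that column. A site using the rule and a site using the illustration would give the same event different dates.

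This matters because the event is always an SAE, so the date in question is an SAE onset date. It is also an event of known interest for this drug. Section 2.2.2 reports, among the three deaths that led to discontinuation at the 18-Dec-2015 data cut, one from HBV reactivation that was considered related to EGF816. A worked example is what site staff are most likely to follow when completing the form.

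**Working it through.** There is no power or sample-size figure to reproduce. The check applies each table's own definition to the example beneath it and counts the days.

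**HCV (Table 6-7)**

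- Definition: new appearance of detectable HCV-RNA. ALT has no part in it.
- Population of the table: known past infection with no detectable HCV-RNA at screening. Detectable RNA also bars entry: "Patients with detectable HCV-RNA are not eligible to be enrolled in the study".
- Facts in the example: RNA detectable on 01-JAN-15; ALT above 5 x ULN on 22-JAN-15.
- The 01-JAN-15 result cannot be a screening result in an enrolled patient, so it is a new appearance. The definition is met by 01-JAN-15.
- Date stated: 22-JAN-15. Difference: 22 − 1 = **21 days**.

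This needs no assumption beyond the population named in the table.

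**HBV (Table 6-6)**

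- Definition: a 1-log rise over screening or newly measurable HBV-DNA (screen-positive row); newly measurable HBV-DNA (screen-negative row). ALT is in neither row.
- HBV-DNA-positive patients may enrol with antiviral therapy (Section 3.1.7 and Section 6.1.3, HBV items 4 and 5).
- Facts in the example: HBV-DNA positive on 01-JAN-15; ALT above 5 x ULN on 01-APR-15. It does not say whether the positivity was new or whether HBV-DNA rose.

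| Reading of the 01-JAN-15 result | Date under Table 6-6 | Date stated | Difference |
|---|---|---|---|
| HBV-DNA newly measurable | 01-JAN-15 | 01-APR-15 | 30 + 28 + 31 + 1 = 90 days |
| Already positive at screening | None follows, as no 1-log rise is given | 01-APR-15 | Cannot be derived |

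On the first reading the date is late. On the second, the example declares a reactivation on a criterion the table lacks. Neither reading agrees with Table 6-6, but only the first yields a number of days.

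**The case against.** The best defence is that the operative rule is right. Both footnotes say the defining laboratory result sets the date, the tables define that result virologically, and the qualifier about signs and symptoms shows that no ALT rise is needed. Only the parenthetical text is wrong, and a careful site would follow the rule. That limits the damage, but it does not remove the contradiction, since the example is there to show how the rule is applied.

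A second defence is that ALT above 5 x ULN prompts viral re-testing. A screen-positive HBV patient re-tested around 01-APR-15 might show a qualifying rise then, which would put the date at or near the one stated. This is possible, but the example mentions no such result. It cannot rescue the HCV example, where the definition was already met.

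A reader might infer more than the documents support:

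- **A delay of 21 to 90 days across both examples.** The 90 days requires newly measurable HBV-DNA, which the example does not state. All the dates are illustrative, so neither figure measures a delay in real patients.
- **A late SAE report.** Section 7.2.3 says an SAE "must be reported to Novartis within 24 hours of learning of its occurrence". That clock runs from awareness, not from onset. Late reporting would follow only if a site waited for the ALT rise before recognising the event.
- **A shifted 21-day resolution period.** The tables use this period to separate restart from restart with PI approval, but no text ties its start to the footnoted reactivation date.
- **A patient without an ALT rise never gets a reactivation date.** That would require a site to ignore both the stated rule and the table heading.
- **Undetectable HCV-RNA confirmed in every enrolled patient.** RNA is tested only after a positive antibody, so the statement holds for Table 6-7's population, which is all the HCV check needs.

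**Conclusion.** The inconsistency is real in both footnotes. Each example dates reactivation by ALT above 5 x ULN, which neither table lists as a defining result and which conflicts with the rule stated just before it. For HCV the stated date is 21 days later than Table 6-7 gives. For HBV the example conflicts with Table 6-6 on any reading, and the gap is 90 days only on the assumption that HBV-DNA was newly measurable on 01-JAN-15.

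The consequence is that SAE onset can be misdated and that sites can date the same event differently. This is a drafting inconsistency affecting an unquantified subset of at most 36 planned patients. It leaves the primary endpoint and sample size untouched and is a minor item. The conclusion rests on the tables as written; whether ALT ought to be part of the definition is a clinical question not judged here.

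**What to change.** Reword the example in each footnote so that it agrees with the defining column of its table and one dating rule remains. In the HBV example, also state the patient's screening status and which criterion in Table 6-6 was met, since the date cannot be derived without them. If the sponsor in fact intended ALT to be part of the definition, the tables and the footnotes would have to be reconciled on that basis, which is for the sponsor's clinical team to decide.

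Make no change to the management actions or to the start of the 21-day resolution period.

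The cost is two footnotes reworded at the next amendment, with no new test or visit. The onset dates of some SAEs may change.
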